## 9 Research Methods

### 9.1 Study Design

Similar to previous postmarketing safety studies conducted with FluMist (Studies FM025 and MI-MA162), this study will be conducted using data collected by the Kaiser Permanente (KP) Vaccine Study Center. In this nonrandomized, observational cohort study, children and adults will be immunized with Q/LAIV as part of routine clinical practice at Northern California Kaiser Permanente (NCKP) sites. Using existing data on healthcare utilization, rates of medically attended events (MAEs) of interest will be evaluated in all eligible Q/LAIV recipients who are vaccinated in the KP Northern California Health Care Plan during the 2013-2014 influenza season. Before the study is completed enrollment must include a minimum of 10,000 children 2 through 8 years of age; based on previous utilization of FluMist at NCKP, enrollment is expected to include approximately 80,000 children and adults 2 to 49 years of age.

Incidence rates of medically attended events (MAEs) and hospitalizations during periods of risk after Q/LAIV vaccination will be compared versus incidence rates during reference periods later in the follow-up (within-cohort analysis) and versus rates in 2 nonrandomized control groups: matched unvaccinated controls and matched concurrent IIV recipient controls identified from the KP healthcare database. Trivalent inactivated vaccine (TIV) recipients will serve as controls along with quadrivalent inactivated influenza vaccine (QIIV) recipients, if a QIIV is approved and administered during the study period.

As observed in previous studies, it is anticipated that children and adults vaccinated with Q/LAIV will differ from those vaccinated with IIV or those unvaccinated in multiple underlying characteristics, such as health-seeking behavior, health status, and various demographic and socioeconomic factors. Within-cohort, risk-interval analysis control helps to control for many of these differences (Farrington et al, 1996; Yih et al, 2011; Andrews, 2002). To help reduce confounding due to differences between Q/LAIV recipients and unvaccinated and IIV controls, controls will be matched to Q/LAIV recipients as discussed below. However, even after matching for these factors, it is likely that other differences between Q/LAIV recipients and IIV control groups will remain and may generate biases in the observed rates of MAEs following vaccination.

The nonrandomized comparison groups will include:

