#### 9.7.4 Multivariable Analysis

One of the primary challenges with performing safety assessment in this setting is that the background rates of many outcomes, such as respiratory events, change over time during the period of vaccination and follow-up. These changes in background rates are due to factors such as patterns in circulation of a variety of respiratory viruses and changes in exposure due to behavior influences such as the school year and holidays.

Controlling for seasonal changes in background rates that are dependent upon calendar time is important to minimize the potential seasonal bias and ensure that the effect of Q/LAIV on the rate of these events from a safety perspective, if any, can be accurately estimated.

The counting-process style of input for the Cox proportional hazards model can accomplish this by allowing the use of calendar time as the structure for defining the observation intervals ([Andersen and Gill, 1982](#)). Rows of observations for each subject will be generally structured as:

*pid, caldtst, caldtsp, event*

where *pid* is the subject identifier, *caldtst* is the calendar date of the beginning of the observation period, *caldtsp* is the calendar date of the end of the observation period, *event* is 1 if an event occurred at the end of the observation period, and 0 if an event did not occur, indicating censoring.

101,	11Oct2013,	22Nov2013,	0
102,	15Oct2013,	02Nov2013,	1

indicates that participant 101 was under observation from October 11 through November 22 and did not experience an event and was censored on November 22. Participant 102 was under observation from October 15 and experienced an event on November 02. Although not shown in this example, the values of main effects and covariates would also be included in each row.

This method controls for the effect of seasonal and other calendar time differences on background event rates because, when each component of the Cox partial likelihood is calculated at each event, the risk set includes only subjects who were under observation during the same calendar time period.

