#### **9.7.4.1 Within-cohort Analyses**

Within-cohort analyses will be conducted among Q/LAIV recipients to see if the incidence of safety outcomes is higher within an immediate post-vaccination “risk” period (eg, 0 to 3, 1 to 14, 15 to 42, and 1 to 42 days post vaccination) compared to later “reference” periods, ie, 7 to 9 days post vaccination for the risk period of 0 to 3 days, 43 to 84 days post vaccination for the risk periods of 1 to 14, 15 to 42, and 1 to 42 days.

This will be accomplished in the Cox models by evaluating the main effect of “period,” defined as a time-dependent variable using the counting-process style of data input. Covariates, stratification factors, and the calendar time structure will be incorporated to control for the effects of age, gender, level of health care utilization, and seasonal difference in background event rates. The main effect variable of “period” will compare post-vaccination “risk” periods to “reference” periods occurring after the risk period.

For each study subject, the beginning of each reference period will follow the end of the risk period.

For example:

*riskperiod03*: 1 = risk (Days 0 through 3)

0 = reference (Days 7 through 9)

*riskperiod142*: 1 = risk (Days 1 through 42)

0 = reference (Days 43 through 84)

If specific results from the primary analyses identify a statistically significant increased risk associated with Q/LAIV administration, additional models with main effects structured to compare the “risk” periods to “reference” periods occurring prior to vaccination may be constructed. To reduce the potential bias associated with the “healthy patient effect,” the reference period prior to vaccination would exclude the week immediately prior to vaccination.

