## **9.9 Limitations of the Research Methods**

This study presents several limitations that are associated with its general design, the data sources, and the study size and power.

Because this study is observational and the decision to vaccinate against influenza is not controlled, the measure of the association between incidence rate of adverse events and vaccination status is exposed to several potential biases, in particular, to an indication bias: subjects who received Q/LAIV may differ from subjects vaccinated with IIV or unvaccinated subjects and present a different risk of adverse events. In order to control for this bias, incidence rates of adverse events of interest during periods at risk after Q/LAIV vaccination will be compared to incidence rates during reference periods later in the follow-up (within-cohort analysis). Additionally, subjects in the two control groups, ie, unvaccinated controls and IIV recipient controls, will be matched with subjects in the Q/LAIV group by age and medical center. Unvaccinated controls will be followed from the date of vaccination of the reference Q/LAIV recipient (ie, the index date). Other potential confounders such as gender and prior health care utilization level will be included as covariates in the proposed Cox proportional hazards model. A complementary analysis will be conducted after exclusion of subjects with high-risk underlying medical conditions.

All the study data are extracted from NCKP clinical and institutional databases; study data can be tracked via an automated audit trail. Databases are thoroughly validated within the Kaiser Permanente system, and are utilized for patient care and management, operational quality assurance, billing, and as a secondary use for research efforts. However, only medically attended events are documented and can be identified according to an ICD-9 diagnosis code, and only a limited number of critical adverse events can be validated against medical chart specifically for this study. Of note, the same limitations apply to adverse events documented during different periods of time, ie, at-risk periods as well as reference periods, and for different subjects, ie, Q/LAIV recipients and matched controls. Therefore, limitations regarding the validity of the data may impact the crude incidence rate estimates of adverse events but should not generate systematic biases of the association between incidence rates and vaccination status.

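### The within-cohort Cox model compares later with earlier vaccinees, never a person with themselves, so residual differences linked to vaccination timing are not removed and are not listed as a limitation

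*Protocol*

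**What the plan says.** Section 9.1 expects Q/LAIV recipients to differ from IIV recipients and unvaccinated persons in "multiple underlying characteristics, such as health-seeking behavior, health status, and various demographic and socioeconomic factors". It continues: "Within-cohort, risk-interval analysis control helps to control for many of these differences". Section 9.9 gives the same analysis a role against indication bias: "In order to control for this bias, incidence rates of adverse events of interest during periods at risk after Q/LAIV vaccination will be compared" with rates in later reference periods.

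Section 9.7.4 sets the model. Time is calendar date, and at each event "the risk set includes only subjects who were under observation during the same calendar time period". Section 9.7.4.1 applies it within the cohort by "evaluating the main effect of “period,” defined as a time-dependent variable using the counting-process style of data input", coded "1 = risk (Days 1 through 42" and "0 = reference (Days 43 through 84", with a parallel coding for days 0-3 and 7-9. On adjustment it says: "Covariates, stratification factors, and the calendar time structure will be incorporated to control for the effects of age, gender, level of health care utilization", and season. The stratification factors are not listed. Section 9.7.3 bases statistical significance on this Cox model and also reports a crude RR.

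**The concern.** Section 9.1 lists mostly stable personal traits, such as care-seeking, health status and socioeconomic position. A comparison of each person's own risk and reference time would cancel such traits. The specified model does not make that comparison. It relies on recent and earlier vaccinees having the same underlying hazard on a given date, after adjustment.

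If people who come early in the season differ from those who come late in ways the covariates miss, the difference goes into the HR for period. With higher-risk people first, the HR is pulled down and a true increase could be masked. With higher-risk people last, it is pulled up and a false signal could appear. The 42-day windows are the exposed ones, and they cover lower respiratory events, wheezing and hospitalization.

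**Working it through.** **1. The plan's own figures.** The protocol gives no figure for timing bias. Its sample-size statements (section 9.5) reproduce: assuming 1:1 groups and two-sided 0.05, power is 88.9% for 10,000 at 1 in 100 and 88.7% for 20,000 at 1 in 200, both with RR 1.5. The rule-out rates are −ln(0.05)/n = 0.030% and 0.015%. This point does not affect them.

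**2. Who is compared with whom.** A person vaccinated on date v contributes risk dates v+1 to v+42 and reference dates v+43 to v+84, which share no date. On date t, the people at risk were vaccinated from t−42 to t−1, and those in reference from t−84 to t−43. The two sides were therefore vaccinated 1 to 83 days apart. For days 0-3 versus 7-9 they were vaccinated 4 to 9 days apart. Stratifying by subject would leave no informative risk set, so no choice of strata makes this model self-controlled.

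**3. Quick size.** Assume that residual hazard, after adjustment, changes by a factor g for each 42 days of later vaccination, and that the true HR is 1. The null HR is then roughly g^(Δ/42), where Δ is the distance between window midpoints:

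- 1-42 vs 43-84: Δ = 63.5 − 21.5 = 42, giving 0.80 (g = 0.8) or 1.25 (g = 1.25)
- 1-14 vs 43-84: Δ = 63.5 − 7.5 = 56, giving 0.74 or 1.35
- 15-42 vs 43-84: Δ = 63.5 − 28.5 = 35, giving 0.83 or 1.20
- 0-3 vs 7-9: Δ = 8 − 1.5 = 6.5, giving 0.97 or 1.04

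**4. Large-sample solution.** Let R(t) and F(t) be the numbers in risk and reference on date t, and r(t) and f(t) their expected events. The Cox estimate θ solves

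Σ over t of [ r(t) − (r(t) + f(t)) · θR(t) / (θR(t) + F(t)) ] = 0.

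Assumed: bell-shaped uptake over 90, 120 or 150 days; background flat or with a threefold winter peak; true HR 1.

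| Residual hazard per 42 days later | 1-42 | 1-14 | 15-42 | 0-3 vs 7-9 |
|---|---|---|---|---|
| No change | 1.00 | 1.00 | 1.00 | 1.00 |
| 10% lower | 0.91-0.93 | 0.88-0.90 | 0.92-0.94 | 0.98 |
| 20% lower | 0.82-0.87 | 0.76-0.80 | 0.84-0.88 | 0.97 |
| 10% higher | 1.07-1.09 | 1.10-1.13 | 1.06-1.08 | 1.01 |
| 25% higher | 1.16-1.22 | 1.26-1.32 | 1.14-1.19 | 1.04 |

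The first three columns use days 43-84 as reference. Even uptake over 90 or 150 days gives 0.81-0.83 (20% lower) and 1.20-1.24 (25% higher) for days 1-42, so the overall ranges are 0.81-0.87 and 1.16-1.24.

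**5. Does conditioning on the person remove it?** In a simulation of 80,000 vaccinees (20 runs, true HR 1), the Cox model gave 1.01, 0.85 and 1.20 for g = 1.0, 0.8 and 1.25. A person-conditional model with two-week calendar effects gave 0.97-1.00 throughout. It is less precise: the SD of the log estimate is about 0.07-0.09, against 0.05-0.06 for Cox.

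**6. Does the crude RR fill the gap?** It has the same people in both windows and equals 1.00 under a flat background. Under the threefold winter peak with bell-shaped uptake and no timing gradient, it falls to 0.56, 0.68 and 0.80 for the 90-, 120- and 150-day spreads (days 1-42). It handles the person but not the season; the Cox model does the reverse.

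**The case against.** Several points on the other side stand.

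- A reader might infer that the protocol promises each person as their own control. It does not. The sentence in section 9.1 is hedged and concerns differences from IIV recipients and unvaccinated persons. Restricting to Q/LAIV recipients does remove vaccine-choice differences. The cited case-series literature is not itself a promise.
- A reader might also infer that the model is unstratified. Section 9.7.4.1 names stratification factors, and listing them can be left to an SAP.
- The most obvious timing differences are partly covered. Prior utilization is adjusted for, although at two levels only (section 9.1). High-risk subjects are analysed separately (sections 9.2.2 and 9.7.1), with a complementary analysis excluding them (section 9.9). As an illustration, suppose the high-risk share fell from 25% to 10% over a 120-day season and went unadjusted. The null HR would be about 0.97, 0.94 or 0.91 if high-risk hazard were 2, 3 or 5 times higher.
- Control of season is a sound priority. Under the assumed winter peak, leaving it out can cost more than a 20% timing gradient does.
- IIV controls vaccinated in the same month and unvaccinated controls followed from an index date roughly balance timing.

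These points narrow the concern without closing it. The matched comparisons bring back the vaccine-choice differences that the within-cohort analysis is meant to avoid. The pre-vaccination reference in section 9.7.4.1 is optional and considered only after a significant increase, so it cannot reveal a masked risk. No planned within-cohort estimate handles both the person and the season.

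**Conclusion.** The point holds in a limited form. The structure follows from the protocol's text: the within-cohort HR that decides significance contrasts people vaccinated at different times, and section 9.9 does not list this. The size rests on an assumed residual timing gradient, for which the documents give no figure. Without a gradient there is no bias. For days 1-42 the null HR is about 0.91-0.93 or 1.07-1.09 for a 10% change, 0.81-0.87 for a 20% decrease and 1.16-1.24 for a 25% increase per 42 days. Days 1-14 are somewhat more exposed, and days 0-3 versus 7-9 hardly at all (0.97-1.04).

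It is tempting to conclude that the study is biased toward apparent safety. The documents do not support that, because the direction depends on which people come early and that is unknown. Nor do they show that the Cox model should be replaced. In a hypothesis-generating study this is an inexpensive improvement and an undisclosed limitation, and it does not invalidate the design.

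**What to change.** Keep the calendar-time Cox model as the deciding analysis. For the 1-42 day contrasts, including 1-14 and 15-42, pre-specify a person-conditional sensitivity analysis on the same windows for lower respiratory events, wheezing, any hospitalization and respiratory hospitalization. A self-controlled case series or conditional Poisson model with calendar-time terms, for example 14-day bins, would do. Treat disagreement with the Cox HR, in either direction, as a flag for timing bias.

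In sections 9.1 and 9.9, state that the Cox contrast is between people vaccinated at different times, and list residual differences between early and late vaccinees as a limitation.

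The cost is one more analysis of existing data, a second and less precise estimate to report, and two short text changes. The analysis would be too sparse to help for rare outcomes such as Guillain-Barré syndrome, and it is not needed for days 0-3 versus 7-9.

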- 1) Inactivated influenza vaccine recipient controls who received the current IIV formulation (trivalent or quadrivalent) but not Q/LAIV for the season at a Kaiser health maintenance organization (HMO) during the same month that the reference Q/LAIV recipient was vaccinated will be identified and matched based on age (year) and medical center relative to concurrent reference Q/LAIV recipients, using frequency matching. For children 2 to 4 years of age, matching by age will be based on calendar quarter of birth rather than year. Factors such as gender and prior health care utilization level will be included as covariates in the proposed Cox proportional hazards model.
- 2) Unvaccinated controls who did not receive any influenza vaccine for the season will be identified and matched based on age (year) and medical center relative to concurrent reference Q/LAIV recipients using frequency matching. For children 2 to 4 years of age, matching by age will be based on calendar quarter of birth rather than year. Factors such as gender and prior health care utilization level will be included as covariates in the proposed Cox proportional hazards model. Unvaccinated controls will be followed from the date of vaccination of the reference Q/LAIV recipient (the index date).

Health care utilization levels will be defined as “high” ( $\geq 2$  visits to a Kaiser HMO within the 6 months prior to the date of vaccination of the reference Q/LAIV vaccinee) or “low” ( $\leq 1$  visit).

The study is expected to begin in the fall of 2013 following the launch of Q/LAIV and to be completed in a single influenza season. However, if fewer than 10,000 Q/LAIV recipients 2 through 8 years of age are identified following the 2013-2014 influenza season, the study will be continued for additional seasons until enrollment of 10,000 Q/LAIV recipients is completed. A detailed description of safety follow-up is described in Section 11. Data will be collected on subjects for 180 days following vaccination (or the index date for unvaccinated controls).

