#### **9.7.4.2 Analyses Versus Matched Controls**

Analyses will be conducted to see if the incidence of safety outcomes is higher among Q/LAIV recipients compared to matched controls (unvaccinated or IIV) within post-vaccination “risk” periods (eg, 0 to 3 days, 1 to 42 days, and 1 to 180 days post vaccination).

This will be accomplished in the Cox models by evaluating the main effect of “treatment group.” Covariates, stratification factors, and the calendar time structure will be incorporated to control for the effects of age, gender, level of health care utilization, and seasonal difference in background event rates.

The main effect variable “treatment group” will be coded as follows:

*Treatment (for unvaccinated control analysis)*: 1 = Q/LAIV, 0 = unvaccinated

*Treatment (for IIV control analysis)*: 1 = Q/LAIV, 0 = IIV

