**2 DOSAGE AND ADMINISTRATION**

**FOR INTRNASAL ADMINISTRATION BY A HEALTHCARE PROVIDER.**

**2.1 Dosing Information**

Administer FluMist Quadrivalent according to the following schedule:

[figure not shown]
Age Group	Vaccination Status	Dosage Schedule
Children age 2 years through 8 years	Not previously vaccinated with influenza vaccine	2 doses (0.2 mL  each, at least 1 month apart)
Children age 2 years through 8 years	Previously vaccinated with influenza vaccine	1 dose (0.2 mL  )
Children, adolescents, and adults age 9 through 49 years	Not applicable	1 dose (0.2 mL  )

Administer as 0.1 mL per nostril.

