**FluMist Quadrivalent in Children and Adolescents**

In the randomized, active-controlled Study MI-CP208 that compared FluMist Quadrivalent and FluMist in children and adolescents 2 through 17 years of age, the rates of solicited adverse reactions reported were similar between subjects who received FluMist Quadrivalent and FluMist. Table 3 includes solicited adverse reactions post Dose 1 from Study MI-CP208 that either occurred at a higher rate (≥ 1% rate difference after rounding) in FluMist Quadrivalent recipients compared to FluMist recipients or were identified in previous FluMist clinical studies (see Table 2). In this study, solicited adverse reactions were documented for 14 days post vaccination. Solicited adverse reactions post Dose 2 were observed at a lower frequency compared to those post Dose 1 for FluMist Quadrivalent and were similar between subjects who received FluMist Quadrivalent and FluMist.

**Table 3: Summary of Solicited Adverse Reactionsa Observed Within 14 Days after Dose 1 for FluMist Quadrivalent and FluMist Recipients in Study MI-CP208b in Children and Adolescents 2 through 17 Years of Age**

Event	FluMist Quadrivalent N = 1341-1377 d	FluMist e N = 901-920 d
	%	%
Runny Nose/Nasal Congestion	32	32
Headache	13	12
Decreased Activity (Lethargy)	10	10
Sore Throat	9	10
Decreased Appetite	6	7
Muscle Aches	4	5
Fever		
> 100°F by any route	7	5
> 100 - ≤ 101°F by any route	3	2
> 101 - ≤ 102°F by any route	2	2

a Solicited adverse reactions that occurred at a higher rate (≥ 1% rate difference after rounding) in FluMist Quadrivalent recipients compared to FluMist recipients or were identified in previous FluMist trials (see Table 2).

b NCT01091246; see www.clinicaltrials.gov

c Represents pooled data from the two FluMist study arms. [See *Clinical Studies (14.2)*]

d Number of evaluable subjects for each event.

In Study MI-CP208, no unsolicited adverse reactions occurred at a higher rate (1% or greater) in FluMist Quadrivalent recipients compared to FluMist recipients.

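### Matched-control analyses neither match on nor name an adjustment for prior influenza vaccination, and at ages 2–8 a second IIV dose may be compared with a first Q/LAIV dose

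*Protocol*

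**What the plan says.** Section 9.1 defines two nonrandomized control groups, both frequency-matched, with age taken as birth quarter at 2–4 years. IIV controls are members who received the current IIV, and not Q/LAIV, "during the same month that the reference Q/LAIV recipient was vaccinated will be identified and matched based on age (year) and medical center". For the other group: "Unvaccinated controls who did not receive any influenza vaccine for the season will be identified and matched based on age (year) and medical center". On covariates it says: "Factors such as gender and prior health care utilization level will be included as covariates in the proposed Cox proportional hazards model". Utilization has two levels: two or more visits in the previous six months, or at most one.

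Section 9.7.4.2 builds the matched-control Cox models "to control for the effects of age, gender, level of health care utilization, and seasonal difference in background event rates". Treatment is a binary term, coded "1 = Q/LAIV, 0 = unvaccinated" in one comparison and in the same way against IIV. Section 9.9 again gives gender and prior utilization as the other confounders.

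Three further places bear on the point:

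- Section 9.1 anticipates that Q/LAIV recipients will differ from both control groups in health-seeking behavior, among other things.
- Section 9.2.1 says that immunizations of plan members are recorded in KITS, the database from which subjects are identified.
- Annex 4, Section 2.1, makes the number of doses at ages 2–8 depend on history. A child "Not previously vaccinated with influenza vaccine" has a two-dose schedule with doses at least a month apart; otherwise it is one dose. Annex 4, Section 6.1, reports: "Solicited adverse reactions post Dose 2 were observed at a lower frequency compared to those post Dose 1 for FluMist Quadrivalent".

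**The concern.** There are two separate gaps.

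**Vaccination history, both comparisons.** All the events compared are medically attended diagnoses or hospitalizations, so a tendency to seek care can raise their recorded rate without any vaccine effect. Earlier influenza vaccination is a recorded marker of that tendency. It may well be distributed differently between people who took Q/LAIV this season and people who took nothing. The planned proxy, a two-level visit count, measures recent contact with care rather than uptake of preventive care, so part of the difference may survive adjustment.

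**Dose number, IIV comparison at ages 2–8.** An IIV control qualifies by having received IIV in the right month, whichever dose of the season it was. A child at a second dose has already had a first dose and come back. If the share of second doses differs between groups, the hazard ratio reflects that mix as well as the vaccine.

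Section 9.7.3 declares increased or decreased risk from the adjusted hazard ratio's confidence limits. A systematic shift can therefore create a signal or hide one. Ages 2–8 are also the group of the postmarketing commitment.

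**Working it through.** **The plan's own figures.** The protocol gives no figure for this bias. Its sample-size statement is not in dispute and reproduces. With 10,000 per group (1:1 assumed, since no ratio is stated), rates of 0.010 and 0.015 and two-sided 0.05, the power is Φ[(0.005 − 1.96 × 0.001571)/0.001571] = Φ(1.22) = 88.9%, against the stated approximately 90%.

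**Is the factor covered anywhere?**

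| Source | Factors named |
|---|---|
| 9.1, IIV matching | month, age, medical center |
| 9.1, unvaccinated matching | age, medical center |
| 9.1 and 9.9, covariates | gender, prior utilization (given as examples) |
| 9.7.4.2, effects controlled | age, gender, utilization, season |

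Vaccination history and dose number are in no row.

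**Size of the bias.** Let a and b be the shares with the factor in the Q/LAIV and control groups, and r the factor's rate ratio on the event after the planned adjustment. With no vaccine effect, the estimated ratio is

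B = [1 + a(r − 1)] / [1 + b(r − 1)].

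The documents give none of a, b or r, so every input below is an assumption.

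- Prior-season vaccination, Q/LAIV versus unvaccinated, a = 0.70, b = 0.20:
  - r = 1.3: 1.21/1.06 = 1.14
  - r = 1.1: 1.07/1.02 = 1.05
- Index dose is a second dose, Q/LAIV versus IIV, a = 0.05, b = 0.20, r = 0.7: 0.985/0.94 = 1.05
- Any factor with a = b: B = 1.00

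Other assumed inputs show that the direction is not known:

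| a, b | r = 0.5 | r = 2 |
|---|---|---|
| 0.40, 0.20 | 0.89 | 1.17 |
| 0.50, 0.20 | 0.83 | 1.25 |
| 0.20, 0.50 | 1.20 | 0.80 |

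**Effect on the decision rule.** Take no true effect, equal groups and a 1-in-100 event. The chance that the lower limit exceeds 1.00 is about Φ[ln(B)/SE − 1.96], with SE = √(1/E₀ + 1/E₁) and E₀, E₁ the control and Q/LAIV event counts. Without bias it is 2.5%.

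- B = 1.14 (unrounded 1.1415), 10,000 per group: E₀ = 100, E₁ = 114, SE = 0.137; Φ(0.966 − 1.96) = 16%. With 20,000 per group: SE = 0.0968; Φ(1.367 − 1.96) = 28%.
- B = 1.05 (unrounded 1.049), 10,000 per group: SE = 0.140; Φ(0.342 − 1.96) = 5%. With 20,000 per group: SE = 0.0988; Φ(0.484 − 1.96) = 7%.

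**Second dose inside the risk window.** A second dose on day 28 to 31 leaves 42 − 28 = 14 to 42 − 31 = 11 post-second-dose days in the 1–42 day window. The protocol does not say whether such a dose starts a new index date, censors follow-up or is ignored. Choosing the first dose as index therefore does not settle the matter by itself.

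**The case against.** The best reply is that the covariate list is open. Sections 9.1 and 9.9 give gender and utilization as examples, and an SAP that is not shown could add vaccination history. Section 9.1 also concedes that differences from IIV controls will probably remain and may bias rates. It offers the within-cohort analysis, where a person's vaccination history cannot differ between periods. The study is hypothesis generating, and signals may be assessed further.

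Much of this is fair, and it limits the weight of the point. It does not remove it. The matching factors and the definition of an IIV control are set in the protocol, and 9.7.4.2 lists the effects to be controlled without this one. A general warning about residual bias is a weak reason to leave out a marker that is already on file. Nor does the within-cohort analysis repair the matched hazard ratios.

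Several stronger statements are tempting but unsupported:

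- *Unvaccinated controls are children who never take influenza vaccine.* They are unvaccinated only for the season and may have been vaccinated before.
- *Dose number changes the study's event rates.* Annex 4 shows lower frequency after dose 2 for solicited reactions to FluMist products only. It shows no dose effect on medically attended events or hospitalizations, none for IIV, and no effect of prior vaccination on any reaction rate.
- *The hazard ratios do mix first and second doses.* The definition permits it; the protocol does not show that it will happen. In the head-to-head trial described in Annex 4, Section 14.1, one rule on the number of doses applied to both vaccines, so the shares could be similar.
- *Twelve months of membership captures the whole preceding season.* A member who joined in mid-fall 2012 and was vaccinated in mid-fall 2013 could have had an early-fall 2012 dose that KITS does not hold.

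**Conclusion.** The point stands in limited form. Prior influenza vaccination is neither matched on nor named for adjustment in either matched-control comparison, although the protocol expects the groups to differ in the behavior that it marks and KITS holds records of it. At ages 2–8 the IIV control definition also lets a second IIV dose stand against a first Q/LAIV dose, and no rule covers a later second dose. Dose number matters only against IIV, because unvaccinated controls have no counterpart.

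The bias cannot be sized from the documents. Under the main assumed inputs a null hazard ratio becomes about 1.05 to 1.14; with equal shares it stays at 1.00, and other inputs reverse the direction. The stated sample-size figures and the within-person comparison of vaccination history are unaffected. The change is worth making because it is cheap and bears on the hazard ratios from which significance is declared, not because a large bias has been shown.

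**What to change.** In Sections 9.1 and 9.7.4.2:

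1. Add recorded influenza vaccination history from KITS as a covariate in both matched-control Cox models. Define it in advance, either as prior season yes/no or as any prior record. The second is closer to the history on which the Annex 4 schedule depends; the first needs less look-back.
2. For the IIV comparison at ages 2–8, use the first influenza vaccine dose of the season as the index dose in both groups.
3. State how a later second dose is handled, identically in both groups: for example, censor at it, or analyse it as a separate dose stratum.

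This takes one derived covariate and two analysis rules, with no new data collection and no change to the sample size. History from before membership or from outside the plan may be missing, so the covariate will be misclassified for some subjects; the report should say so. A few children whose first dose of the season was the other vaccine drop out of the IIV comparison, and censoring at the second dose would shorten some follow-up.
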